7.10.4.4. Analysis Methods

Two ANCOVA models will be used, one to compare the mean change in office systolic blood pressure and one to compare the mean change in diastolic blood pressure from baseline to 6 months between the study arms after adjusting for the baseline measurement.

For change in office systolic blood pressure, the ANCOVA model will include the change measurement (as defined in 3.4.1.2) from baseline to the 6-month follow-up visit as the response and study arm indicator and baseline office systolic measurement as covariates.

For change in office diastolic blood pressure, the ANCOVA model will include the change measurement (as defined in 3.4.1.2) from baseline to the 6-month follow-up visit as the response and study arm indicator and baseline office diastolic measurement as covariates.

Code similar to the following can be used for the ANCOVA models:

```
PROC MIXED DATA = Data;
  CLASS trtGroup;
  MODEL change_measure = trtGroup baseline_measure;
  RUN;
```

7.10.4.5. Datasets Analyzed

The mITT analysis set will be used for this objective.

7.10.4.6. Subgroup Analyses

The subgroups to be analyzed are defined in section 7.9. Two ANCOVA models will be constructed for each endpoint, one for each subgroup set; 1) AF diagnoses, and 2) pulmonary vein isolation. The models will include covariates for subgroup and the interaction between subgroup and treatment.

Code similar to the following can be used for the ANCOVA models:

```
PROC MIXED DATA = Data;
  CLASS trtGroup subgroup;
  MODEL change_measure = trtGroup subgroup trtGroup*subgroup
  baseline_measure;
  RUN;
```

Example: In the AF diagnoses analysis, subgroup will equal 0 if AF diagnosis is paroxysmal and subgroup will equal 1 if AF diagnosis is persistent

7.10.5. Ancillary #2: Heart rate at 6 months compared to baseline

Compare the difference of heart rate at 6 months and baseline between study arms.

7.10.5.1. Hypothesis

There is no pre-specified hypothesis for this objective.

7.10.5.2. Performance Criteria and Rationale

There are no performance criteria for this objective.

7.10.5.3. Endpoint Definition

The endpoint for this objective is defined as the difference in heart rate in a given subject between the 6-month follow-up measurement and the baseline measurement

- For example: for subject 11111, the 6-month measure is 70 bpm and the baseline measure is 75 bpm so the endpoint value is -5 bpm (70 minus 75).

Source variables

- Baseline heart rate: VSORRES_HR from Baseline CRF Section E
- 6-month heart rate: VSORRES_HR from MONTH 6 FOLLOW UP CRF Section B

7.10.5.4. Analysis Methods

An ANCOVA model will be used to compare the mean change in heart rate from baseline to 6 months between the study arms after adjusting for baseline heart rate. The ANCOVA model will include the change measurement (as defined in 7.10.5.3) from baseline to the 6-month follow-up visit as the response and study arm indicator and baseline heart rate measurement as covariates.

Code similar to the following can be used for the ANCOVA models:

```
PROC MIXED DATA = Data;
  CLASS trtGroup;
  MODEL change_measure = trtGroup baseline_measure;
RUN;
```

7.10.5.5. Datasets Analyzed

The mITT analysis set will be used for this objective.

7.10.5.6. Subgroup Analyses

The subgroups to be analyzed are defined in section 7.9. Two ANCOVA models will be constructed, one for each subgroup set; 1) AF diagnoses, and 2) pulmonary vein isolation. The models will include covariates for subgroup and the interaction between subgroup and treatment.

Code similar to the following can be used for the ANCOVA models:

```
PROC MIXED DATA = Data;
  CLASS trtGroup subgroup;
  MODEL change_measure = trtGroup subgroup trtGroup*subgroup
    baseline_measure;
RUN;
```

7.10.6. Ancillary #3: Procedural measures

Compare procedural measures between study arms.

7.10.6.1. Hypothesis

There is no pre-specified hypothesis for this objective.

7.10.6.2. Performance Criteria and Rationale

There are no performance criteria for this objective.

7.10.6.3. Endpoint Definition

The following procedure measures endpoints will be reported for each study arm:

- total procedure time

- Calculate total procedure time for each subject: Add cryoablation procedure time and renal artery denervation procedure time as defined below
- cryoablation procedure time
 - Start time: Time of first cryocatheter insertion (PROCTIME2 from CARDIAC CRYOABLATION PROCEDURE CRF Section C question 3)
 - End time: Time of last ablation catheter removal (PROCTIME5 from CARDIAC CRYOABLATION PROCEDURE CRF Section F question 2)
- renal artery denervation procedure time
 - Start time: Time of renal denervation catheter insertion (IMSTTM2 from RENAL DENERVATION PROCEDURE CRF Section C question 4)
 - End time: Time of renal denervation catheter removal (SPDUR1 from RENAL DENERVATION PROCEDURE CRF Section E question 3)
- ablation time
 - Cryoablation procedure
 - Sum of duration of each energy application (SEC) for a subject on the ENERGY APPLICATION CRF (unit of interest is a subject)
- fluoroscopy time
 - Cryoablation procedure
 - Elapsed fluoroscopy time at end of the cryoablation procedure (PROCTIME6)
- dye usage
 - Cryoablation procedure
 - Type of contrast used during procedure (IMP_GENERSED2)
 - Amount of contrast used (CONCERNTRATE1)
 - Concentration of contrast used (CONSERNTRATE2)
 - Renal artery denervation procedure
 - Type of contrast used during the procedure (SPORRESC)
 - Amount of contrast used (DPORRESN)
 - Concentration of contrast used (SPORRESN)

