### 6.12 Renal angiography

Perform renal angiography if randomized to Treatment, following the pulmonary vein isolation procedure.

Subjects should be prepped for a renal angiography according to standard procedures. For subjects with chronic kidney disease and/or risk factors for contrast-induced nephropathy (CIN), the hospital's standard-of-care protocol for CIN prevention should be utilized.

An aortogram and selective renal angiography will be performed to confirm renal artery anatomy. Anatomic eligibility is defined as each kidney having at least one renal artery  $\geq 3$ mm and  $\leq 8$ mm in diameter and minimum treatable length per the Symplicity Spyral Catheter Instructions for Use, without significant stenosis or other abnormality. *NOTE: All renal arteries with  $\geq 3$  mm and  $\leq 8$ mm diameter with minimum treatable length per the Symplicity Spyral Catheter Instructions for Use shall be*

*treated, including dual renal arteries meeting these morphologic criteria.*

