### **6.13 Renal artery denervation procedure**

If randomized to Treatment, the renal artery denervation procedure will be performed according to the supplied Symplicity Spyral Catheter Instructions for Use, Symplicity G3 Generator User Manual and associated training provided by Medtronic.

Prior to this procedure, appropriate systemic anticoagulation and sedation should be attained. Blood pressure and heart rate should be closely monitored throughout the procedure. Investigators may choose to apply treatment to any renal artery that meets the anatomy eligibility criteria. The Symplicity Spyral Catheter will be delivered to the renal artery and the ablation treatments at multiple positions along the renal artery will be performed according to the procedures described in the Instructions for Use.

Provide one copy of the renal angiogram cine procedure to Medtronic.

Sedation type, procedure information, fluoroscopy time, contrast dye amount and concentration will be collected.

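### The Ancillary #3 fluoroscopy comparison covers only the cryoablation step, so it cannot show the fluoroscopy that denervation adds; the total procedure time also leaves out the Treatment-only angiography

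*SAP*

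**What the plan says.** Protocol 12.6 lists procedural measures among the ancillary endpoints to be compared between arms. Fluoroscopy time, ablation time and total procedure time are named without further definition or limit. SAP 7.10.6.3 supplies the definitions.

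- **Fluoroscopy time:** one entry, under a cryoablation sub-heading: "Elapsed fluoroscopy time at end of the cryoablation procedure (PROCTIME6". There is no denervation entry.
- **Ablation time:** also cryoablation only.
- **Dye usage:** separate cryoablation and denervation entries.
- **Total procedure time:** "Add cryoablation procedure time and renal artery denervation procedure time as defined below".

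SAP 7.10.6.4 compares the continuous measures between arms by t-test, or by Mann-Whitney if normality fails. On the data side, Protocol 6.10.5 collects fluoroscopy time for the pulmonary vein isolation, and Protocol 6.13 does so again for denervation: "Sedation type, procedure information, fluoroscopy time, contrast dye amount and concentration will be collected".

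**The concern.** The study exists to assess the feasibility of doing both procedures in the same patient (Protocol 1.1). Extra fluoroscopy and extra session time are direct outputs of that question, and Protocol 10 names radiation from both procedures as a risk to subjects. A fluoroscopy comparison that stops when cryoablation stops measures nothing that differs by design between the arms. If it were reported as a between-arm result, a reader planning a pivotal trial could take a null finding as evidence that denervation adds no fluoroscopy.

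Nothing marks the restriction as deliberate. Dye usage in the same list covers both procedures, and SAP 7.13, which explains one departure from the Protocol, does not mention this one.

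**Working it through.** The documents give no expected minutes, standard deviation or power for Ancillary #3, so there is no stated figure to reproduce. The check sets the SAP time points against the procedure sequence in the Protocol.

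**Fluoroscopy**

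1. Write C for fluoroscopy up to the end of cryoablation, and F for fluoroscopy during renal angiography and denervation (Treatment only).
2. The SAP compares E[C | Treatment] − E[C | Control]. The full contrast is E[C + F | Treatment] − E[C | Control].
3. Under Protocol 6.9, subjects and center personnel do not know the assignment until isolation is finished. C is therefore measured over the same step in the same conditions, and the SAP difference has expectation of about zero whatever F is. It is only about zero because the modified intention-to-treat set removes some Treatment subjects after isolation (Protocol 12.2; SAP 7.1.3).
4. As an illustration, take 35 per arm (70 at 1:1), a two-sided 0.05 test (assumed; the SAP sets no level for this objective) and a common SD in both arms (assumed). Let d be the added fluoroscopy in SD units. Power = Φ(d/√(2/35) − 1.96) + Φ(−d/√(2/35) − 1.96), with √(2/35) = 0.239.

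| Assumed added fluoroscopy (SD) | Rejection rate, SAP definition | Power, cryoablation + denervation total |
|---|---|---|
| 0.25 | about 5% | 18% |
| 0.5 | about 5% | 55% |
| 0.75 | about 5% | 88% |
| 1.0 | about 5% | 99% |

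**Total procedure time**

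1. The first interval runs from first cryocatheter insertion (PROCTIME2) to "End time: Time of last ablation catheter removal (PROCTIME5 from CARDIAC CRYOABLATION PROCEDURE CRF Section F question 2".
2. The second interval runs from "Start time: Time of renal denervation catheter insertion (IMSTTM2 from RENAL DENERVATION PROCEDURE CRF Section C question 4" to "End time: Time of renal denervation catheter removal (SPDUR1 from RENAL DENERVATION PROCEDURE CRF Section E question 3".
3. Protocol 6.12 says "Perform renal angiography if randomized to Treatment, following the pulmonary vein isolation procedure", and describes the content: "An aortogram and selective renal angiography will be performed to confirm renal artery anatomy". The step follows isolation and checks anatomy for denervation, so by its order and purpose it lies between the two intervals and enters neither. Protocol 9.1 (Table 8) likewise gives the renal angiogram its own timing category.
4. Let D be denervation catheter time and G the gap from PROCTIME5 to IMSTTM2. The SAP counts D as the added time; the elapsed addition is D + G. The share missed is G/(D + G).
5. With assumed values of D from 20 to 60 minutes and G from 10 to 40 minutes, the share runs from 10/70 = 14% to 40/60 = 67%. That width shows that the documents do not fix the size.

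**The case against.** The strongest reply is that the added burden is largely on display. Denervation procedure time is an endpoint of its own and is included in the total, and denervation contrast type, amount and concentration are reported. This is correct. A reader might infer that the plan hides the burden of denervation, but the documents do not support that. What is missing is the denervation fluoroscopy and the angiography interval.

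Second, the total-time rule is explicit and reproducible, and Protocol 12.6 does not define the term, so the SAP contradicts nothing. Measuring first to last catheter would count idle time between procedures and would still omit vascular access before the first cryocatheter and the Reveal LINQ insertion. This also stands. The sum is not an error in itself; it is a catheter time carrying a label that suggests session time.

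Third, the fluoroscopy entry sits under a cryoablation sub-heading, so its scope is visible, and SAP 3 says the plan does not limit what may be reported. That softens the omission but does not cure it: the prespecified comparison still cannot answer its question, and an optional extra analysis does not replace it.

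Fourth, no denervation fluoroscopy variable is named in the SAP, and the CRFs are not part of the documents. The field may exclude angiography, or it may be a running reading that already contains the cryoablation part. This stands and limits how the fix can be worded.

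**Conclusion.** The fluoroscopy definition is wrong for its purpose. The denervation component is entirely absent from the comparison, the expected difference is about zero, and the test rejects at about its nominal rate however large the true addition. This rests on the blinding in Protocol 6.9 holding through isolation. A reader might go further and say the analysis is bound to report no difference. It is not: chance rejections of about 5% remain, and the post-isolation exclusions mean the arms are not exactly as randomized.

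The total-time point is secondary. Treatment session time is understated by at least the angiography, by an amount the documents do not give; the 14% to 67% range rests wholly on assumed minutes. The restriction of ablation time to cryoablation is of the same kind.

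The stakes are modest. SAP 7.10.6.1 and 7.10.6.2 set no hypothesis and no performance criterion, and no primary result, secondary result or stopping decision changes. The point merits correction because it bears on the stated feasibility question and is cheap to put right.

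**What to change.** 1. **Fluoroscopy.** Define the per-subject total as PROCTIME6 plus the denervation fluoroscopy collected under Protocol 6.13; in Control the total is PROCTIME6 alone. Compare totals between arms and report the components as separate rows. First check on the CRF whether the denervation field includes the renal angiography and whether it is cumulative. If it is cumulative from the start of the session, use it as the total and do not add PROCTIME6. If it excludes angiography, say so in the row label.
2. **Total time.** Keep the existing sum but label it catheter time. Add elapsed time from PROCTIME2 to SPDUR1 in Treatment and from PROCTIME2 to PROCTIME5 in Control, with a note that the Treatment figure includes any idle time between procedures.
3. **Ablation time.** Add the denervation energy time if it is recorded; otherwise label the row as cryoablation only.

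The cost is SAP wording and a few derivations. Every time stamp for item 2 is already named in SAP 7.10.6.3. Items 1 and 3 depend on the CRF check; Protocol 6.13 supports the collection of denervation fluoroscopy, but the documents do not show the field.

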7.10.6.4. Analysis Methods

The procedure measure endpoints will be compared between study arms in order to further characterize the differences in outcomes between patients randomized to pulmonary vein isolation only and patients randomized to pulmonary vein isolation and renal artery denervation. Mean, standard deviation, median, and range will be used as descriptive statistics for continuous variables and counts and proportions for

categorical variables. T-tests will be used to test continuous endpoints between study arms. The Mann-Whitney test (a.k.a, Wilcoxon rank sum test) may be used if normality assumptions are not met. Fisher's exact test will be used to test categorical endpoints between study arms.

7.10.6.5. Datasets Analyzed

The mITT analysis set will be used for this objective.

7.10.6.6. Subgroup Analyses

No subgroup analyses are planned for this objective.

7.10.7. Ancillary #4: Symptoms at 6 months compared to baseline

Compare the presence of symptoms at 6 months between study arms.

7.10.7.1. Hypothesis

There is no pre-specified hypothesis for this objective.

7.10.7.2. Performance Criteria and Rationale

There are no performance criteria for this objective.

7.10.7.3. Endpoint Definition

The endpoints for this objective are presence of the following symptoms as recorded at the 6-month visit:

- Dizziness
- Palpitations
- Rapid heart beat
- Dyspnea
- Fatigue
- Syncope
- Other

7.10.7.4. Analysis Methods

A logistic regression model will be used with presence of each symptom at 6 months as the response and study arm indicator and baseline presence of symptom as covariates. An alpha of 0.05 will be used to

determine the significance of each covariate. Odds ratios and their corresponding 95% confidence intervals will be reported for each covariate to characterize their estimated effect on the response.

Code similar to the following can be used for the logistic regression models:

```
PROC LOGISTIC DATA = Data;
  CLASS trtGroup;
  MODEL Endpoint = trtGroup symptom_at_baseline / expb;
  RUN;
```

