### 5.2.2 Exclusion criteria

- Active systemic infection
- Cryoglobulinemia
- One or more pulmonary vein stents
- Type I Diabetes
- NYHA Class IV heart failure with in the past 6 months
- Renal artery anatomy that is ineligible for treatment including:
  - Lacks at least one renal artery for each kidney with  $\geq 3$  mm and  $\leq 8$  mm diameter and minimum treatable length per the Spyral Instructions for Use prior to a significant arterial branch (*NOTE: All renal arteries with  $\geq 3$  mm and  $\leq 8$  mm diameter with minimum treatable length per the Spyral Instructions for Use shall be treated, including dual renal arteries meeting these morphologic criteria.*)
  - Renal artery stenosis ( $>50\%$ ) or renal artery aneurysm in either renal artery
  - A history of prior renal artery intervention including balloon angioplasty or stenting
  - Renal artery which contain calcification which does not allow at least four radio frequency ablations to be delivered
  - Diffuse fibromuscular dysplasia (FMD) or FMD which does not allow at least four radio frequency ablations to be delivered; FMD defined as visible beading of the artery on angiography
  - Unilateral kidney
- Estimated Glomerular Filtration Rate (eGFR) of  $<30$  mL/min/1.73m^2
- Primary pulmonary hypertension
- Pheochromocytoma, Cushing's Disease, coarctation of the aorta, untreated hyperthyroidism, primary hyperparathyroidism or hyperaldosteronism (Note: treated hyperthyroidism is permissible)
- Myocardial infarction, unstable angina pectoris, syncope, PCI/PTCA, or coronary artery stenting within 3 months prior to signing the consent form, or has widespread atherosclerosis with documented intravascular thrombosis or unstable plaques
- Cerebrovascular accident or TIA within 1 month prior to signing the consent form
- Prior ablation for atrial fibrillation in the left atrium
- Presence of a permanent pacemaker, biventricular pacemaker, atrial defibrillator or any type of implantable cardiac defibrillator (with or without biventricular pacing function)
- Cardiac valve stenosis for which a significant reduction of blood pressure is contraindicated
- A condition that would prohibit or interfere with ability to obtain an accurate blood pressure measurement using the protocol-specified automatic blood pressure monitor (e.g., arm diameter too large for the cuff)

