5.3. Randomization and Blinding

Randomization schedules will be prepared for each site using a random permuted block design stratified by center and AF diagnosis. The schedules will allocate subjects in a 1:1 ratio to the treatment or control arm. Each center will receive a set of sequentially numbered envelopes labeled specifically for that center that is labeled with one randomization code per envelope. After a CT scan has been performed and confirmed that the renal anatomy meets eligibility requirements, the subject will be randomized. The next sequential envelope labeled with a randomization code will be used. The envelope number will be recorded for each randomized subject and communicated to Medtronic. The sequence of subject randomization will be checked to ensure it matches the sequence of envelope numbers.

Randomization assignments are the following:

- Treatment:
 - Perform the pulmonary vein isolation procedure, renal angiogram, renal artery denervation procedure and the Reveal LINQ insertion.
- Control:
 - Perform the pulmonary vein isolation procedure and the Reveal LINQ insertion. Do NOT perform renal denervation.

Enrolled subjects who were not randomized should be exited. Subjects and center personnel will be blinded to the randomization assignment until after the pulmonary vein isolation procedure. Randomization envelopes may be returned to the randomization pool if the patient is exited before revealing the randomization assignment to center personnel. Crossing over to the Treatment group once assigned to the Control group is not allowed at any point during the study.

Medtronic statisticians are planning to conduct the analyses for this study. Analyses using actual randomization assignments will not be performed until after the final database freeze except for interim analyses or analyses performed for the DMC. Unblinding for the DMC will be considered planned unblinding. The freeze intended for the final report will also be considered a planned unblinding.

Analyses of the study objectives for review by the DMC will be performed by a Medtronic statistician other than the lead statistician for the study. The lead study statistician will be blinded to all DMC analyses of study objectives. The unblinded statisticians will keep results strictly confidential per the DMC charter during the study.

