5.6. Data Monitoring Committee

A DMC will periodically review accumulating safety data for the study, including the rate of safety composite events within each study arm and the difference in the rate between study arms (i.e., the Primary Safety Objective).

6. Determination of Sample Size

The overall study sample size is 70 randomized subjects that undergo a pulmonary vein isolation procedure which is the required sample size for the primary effectiveness objective.

Subjects that are enrolled in the study may not go on to be randomized due to a variety of reasons, including elective withdrawal prior to randomization, blood pressure measurements that do not meet study criteria, or renal anatomy that is found to be ineligible upon angiography. Based on the rate of randomization among enrolled subjects in trials with similar screening criteria, up to 245 subjects may need to be enrolled and undergo screening in order to ensure that 70 subjects are randomized.

There will be at least 78% power to test the primary effectiveness objective provided at least 70 subjects undergo randomization and undergo a pulmonary vein isolation procedure. Table 1 below shows the expected incremental power at each analysis. The first and second look correspond to the interim analyses. The third interim look is the final analysis.

Table 1: Power at each stage of the analyses

Look	Patients w/ six month follow-up	Expected Incremental Power of Analysis
1	32	17.6%
2	50	10.1%
3	70	50.9%
Cumulative Power:		78.6%

Subjects who are randomized and meet either of the following two conditions do not count toward the 70 randomized subjects to be used in the mITT set (define below):

- Exit the study without undergoing a pulmonary vein isolation procedure
- Subjects who are randomized to the treatment group and are found not to meet inclusion/exclusion criteria during the renal denervation procedure

The sample size calculation is based on the following assumptions:

- 1:1 randomization
- Constant randomization rate over 16 months
- Last enrolled subject followed through 6 months post-procedure
- 50% chronic treatment success in the Control arm (PVI only) versus 75% in the Treatment arm (equivalent to a hazard ratio of 0.415) through 6 months post-procedure
- Constant hazard ratio over all follow-up
- Constant attrition (dropout) of 5% per 6 months

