7.10.7.5. Datasets Analyzed

The mITT analysis set, excluding subjects without the 6-month visit, will be used for this objective.

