7.10.7.6. Subgroup Analyses

The subgroups to be analyzed are defined in section 7.9. A logistic regression model will be constructed each subgroup. The model will include covariates for subgroup and the interaction between subgroup and treatment.

Code similar to the following can be used for the logistic regression models:

```
PROC LOGISTIC DATA = Data;
  CLASS trtGroup subgroup;
  MODEL Endpoint = trtGroup symptom_at_baseline subgroup
    trtGroup*subgroup / expb;
  RUN;
```

7.10.8. Ancillary #5: Freedom from chronic treatment failure and off Class I and III anti-arrhythmic drugs following the blanking period

Compare the rate of chronic treatment success (primary effectiveness endpoint) between study arms for subjects off of Class I and III anti-arrhythmic drugs following the blanking period.

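### The symptom models have no sparse-data rule, so for a rare symptom such as syncope the planned odds ratio would often have no finite estimate

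*SAP*

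**What the plan says.** SAP 7.10.7.3 defines seven binary endpoints as "presence of the following symptoms as recorded at the 6-month visit". The list includes syncope and an open category for other symptoms.

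SAP 7.10.7.4 gives the model: "A logistic regression model will be used with presence of each symptom at 6 months as the response and study arm indicator", plus presence of the same symptom at baseline. It promises an odds ratio and 95% confidence interval for both covariates. The sample code is a default PROC LOGISTIC call with no penalised or exact option. SAP 7.10.7.6 extends this to subgroups: "The model will include covariates for subgroup and the interaction between subgroup and treatment". SAP 7.9 names two subgroup factors, AF diagnosis and RF touch-up.

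The analysis set is restricted: "The mITT analysis set, excluding subjects without the 6-month visit, will be used for this objective".

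Protocol (CIP) 12.6 specifies the same main model. It also plans counts and proportions for categorical ancillary endpoints. Neither document sets a minimum event count or an alternative for sparse symptoms. For the procedural measures, by contrast, SAP 7.10.6.4 names Fisher's exact test for categorical endpoints and a rank test as a fallback for continuous ones.

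**The concern.** When one arm has no events, the logistic likelihood keeps rising as the arm coefficient goes to plus or minus infinity. Software still prints a result, but it is an arbitrary large number with a huge standard error, and the Wald interval carries no information. The baseline coefficient fails in the same way if, for example, no baseline-positive subject has the symptom at 6 months. It does not exist at all if no analysed subject had the symptom at baseline.

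Syncope is the symptom for which the documents give some reason to expect this. CIP 5.2.2 excludes "Myocardial infarction, unstable angina pectoris, syncope, PCI/PTCA, or coronary artery stenting within 3 months prior to signing the consent form", so recent syncope should be uncommon at entry.

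What is at stake is small but avoidable. For a sparse symptom the analyst would report an uninformative odds ratio or choose another method after seeing the data.

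**Working it through.** **Inputs.** SAP section 6: "The overall study sample size is 70 randomized subjects that undergo a pulmonary vein isolation procedure". SAP 5.3: "The schedules will allocate subjects in a 1:1 ratio to the treatment or control arm". That gives 70/2 = 35 per arm. SAP section 6 also assumes "Constant attrition (dropout) of 5% per 6 months", so with the 6-month-visit restriction about 35 × 0.95 = 33 per arm remain. No symptom rate is stated at baseline or at 6 months; every rate below is an assumption, and equal rates in the two arms are assumed.

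**The plan's own figure.** None exists for this objective. N = 70 comes from the primary effectiveness test, whose stated power (17.6% + 10.1% + 50.9% = 78.6%) is reproduced by simulating the three looks at 14, 19 and 41 events with the stated boundaries and a hazard ratio of ln(0.75)/ln(0.50) = 0.415. That sample size was not chosen with symptoms in mind.

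**Arm odds ratio.** With n per arm and 6-month rate p, P(no events in at least one arm) = 1 − (1 − (1 − p)^n)². For p = 5% and n = 35: 0.95^35 = 0.166; 1 − 0.166 = 0.834; 0.834² = 0.695; 1 − 0.695 = 0.305.

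| Assumed 6-month rate | 35 per arm | 33 per arm |
|---|---|---|
| 1% | 91% | 92% |
| 2% | 74% | 76% |
| 3% | 57% | 60% |
| 5% | 30% | 33% |
| 10% | 5% | 6% |
| 20% | 0.1% | 0.1% |

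If only the 50 or 32 subjects of an interim look were analysed (25 or 16 per arm), the 5% row would become 1 − (1 − 0.95^25)² = 48% or 1 − (1 − 0.95^16)² = 69%.

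**No events in either arm.** This case is included above and equals (1 − p)^70: 49% at 1%, 12% at 3%, 3% at 5%.

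**The full models.** An odds ratio is promised for the baseline term too, so the arm calculation understates the problem. The specified models were simulated with 35 per arm, 3,000 runs per setting and a baseline-symptom odds ratio of 1 or 3, checking each dataset for separation or a constant covariate. The subgroup model assumes 30% of subjects in the smaller subgroup; the documents do not give this split. The table shows the percentage of trials in which at least one odds ratio in the model has no finite estimate.

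| 6-month rate / baseline rate (assumed) | Main model | Subgroup model |
|---|---|---|
| 2% / 2% | 97–99% | essentially all |
| 5% / 5% | 74–89% | 96–98% |
| 5% / 10% | 56–76% | 93–96% |
| 10% / 20% | 11–26% | 65–71% |
| 20% / 40% | below 1% | 21–24% |
| 40% / 70% | below 1% | 2–3% |

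At a 2% baseline rate, about a quarter of trials have no baseline-positive subject, which agrees with 0.98^70 = 24%.

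**The case against.** The strongest reply is that little is lost. Ancillary #4 has no hypothesis and no performance criterion (SAP 7.10.7.1 and 7.10.7.2), and SAP 7.9 calls the subgroup comparisons exploratory. The code is offered only as an example, so a penalised fit is not ruled out, and CIP 12.2 and SAP 7.13 require method changes to be justified in the study report. All of this stands and sets the priority. It does not supply a rule fixed in advance: disclosing a substitute afterwards is not the same as specifying it.

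A reader might infer that results for a sparse symptom would be missing. They would not. A split such as 0/35 against 2/35 would still appear as counts and proportions under CIP 12.6; only the model odds ratio and its interval would be uninformative.

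A reader might also infer from the exclusion criterion that the baseline syncope covariate must be nearly constant. The exclusion covers only the 3 months before consent. CIP 6.8 collects AF history and symptoms at baseline without a look-back period, so older syncope could count as present. Nor does the exclusion fix the 6-month rate, which drives the zero-event calculation. It makes syncope the likely case, not a certain one.

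**Conclusion.** The point holds for rare symptoms. At assumed 6-month rates of 5% or less with 35 per arm, the arm odds ratio has no finite estimate in roughly 30% to 91% of trials, and the main model fails on at least one promised odds ratio more often than that. The interaction models fail at higher symptom rates than the main model, still about one time in five at 20% under the assumed 30% subgroup share.

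It does not extend to all seven symptoms, tempting as that is with so few subjects. Entry requires symptomatic AF, and nothing in the documents suggests that palpitations, rapid heart beat, dyspnea, fatigue or dizziness are rare; the open category cannot be judged. In the simulated settings with rates of 20% or more, the main model is almost always estimable.

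The size depends on the assumed rates, equal rates in the arms and the assumed subgroup split. The primary analysis and the sample size are not affected. Low priority.

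**What to change.** In SAP 7.10.7.4 and 7.10.7.6, specify Firth penalised logistic regression with profile-likelihood confidence intervals for all the symptom models. Add two rules:

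- Omit the baseline term only when it is constant among the analysed subjects. Firth handles a sparse covariate but not a constant one. A wider rule, such as dropping the term below some count of baseline positives, would be largely redundant and would depart from the model in CIP 12.6.
- Report counts only when neither arm has an event, because Firth would then return an uninformative odds ratio near 1.

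This stays within the planned logistic model and its covariates, apart from the case where a covariate cannot be fitted. The cost is a model option, the two rules above and slight shrinkage of the estimates toward no effect.
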